2.1.1. Primary Estimand (Estimand 1)

The primary estimand of the main study is a composite estimand, which estimates the effect of randomized treatment accounting for treatment adherence and response.

- Population: Participants with moderate-to-severe Atopic Dermatitis (AD) as defined by the inclusion criteria to reflect the targeted participant population;
- Variable: Response based on the Investigator's Global Assessment (IGA) score of clear (0) or almost clear (1) and a reduction from baseline of ≥ 2 points at Week 12; for participants who drop out for any reason the outcome will be defined as “non-responsive” after that point;
- Intercurrent event: The intercurrent event is captured through the variable definition;
- Population-level summary: Proportion of participants who are responders in each treatment group and differences in proportions of responders between each PF-04965842 dose and placebo.

Estimand 1 composite estimand is the primary estimand for the co-primary and key secondary endpoints: IGA response at Week 12, EASI-75 at Week 12, and PP-NRS4 at Weeks 2, 4, and 12. Other binary outcome measures such as response based on IGA, EASI-75 and PP-NRS4 at all other scheduled timepoints, % BSA <5%, EASI-50, EASI-90, EASI-100, SCORAD50, and SCORAD75 will follow the same structure.

2.1.2. Secondary Estimand(s)

2.1.2.1. Hypothetical Estimand (Estimand 2)

The secondary estimand of this study is a hypothetical estimand, which estimates the effect as if all patients maintain their randomized treatment.

090177e19618b8f5\Approved\Approved On: 25-Jan-2021 08:47 (GMT)

- Population: Participants with moderate-to-severe AD as defined by the inclusion criteria to reflect the targeted participant population;
- Variable: Change from baseline in Pruritus and Symptoms Assessment for Atopic Dermatitis (PSAAD) total score at Week 12;
- Intercurrent event: All data collected will be utilized;
- Population-level summary: Difference in least-square means between each PF-04965842 dose and placebo.

Change from baseline or Percent change from baseline to each specific post baseline scheduled time points in a continuous outcome measure such as total scores obtained from EASI, NRS, SCORAD, %BSA, PtGA, HADS, POEM, CDLQI, EQ-5D-Y, DFI, Peds FACIT-F will follow the same structure as defined for PSAAD.

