9. STATISTICAL CONSIDERATIONS

9.1. Estimands and Statistical Hypotheses

9.1.1. Estimands

The primary estimand of the main study is a composite estimand (accounting for both treatment adherence and response), defined according to the primary objective and is in alignment with the primary endpoint. It includes the following four attributes:

- Population: Participants with moderate-to-severe AD as defined by the inclusion criteria and exclusion criteria and are randomized;
- Variable: Response based on IGA and EASI-75 at Week 12 (co-primary endpoints) and any other binary outcome measures such as response based on NRS4, % BSA < 5%, EASI-50, EASI 90, EASI-100, SCORAD50, SCORAD75. Participants who discontinue from the study treatment for any reason are considered as treatment failures or non-responders;
- Intercurrent event: The intercurrent event is captured through the variable definition;
- Population-level summary: Proportion of participants who are responders in each treatment group and differences in proportions of responders between each PF-04965842 dose and placebo at Week 12.

The secondary estimand of this study is the hypothetical estimand, which estimates the effect as if all patients maintain their randomized treatment. It includes the following four attributes:

- Population: Participants with moderate-to-severe atopic dermatitis as defined by the inclusion criteria for the double-blind phase and are randomized;
- Variable: Change from baseline to Week 12 in a continuous outcome measure such as total scores obtained from EASI, NRS, SCORAD, %BSA, PSAAD, PtGA, HADS, POEM, CDLQI, EQ-5D-Y, DFI, Peds FACIT-F;
- Intercurrent event: All data after an intercurrent event (eg discontinuation of treatment), if collected, will be censored;
- Population-level summary: Difference in least-square means between each PF-04965842 dose and placebo.

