9.4.2.2. Analysis of Secondary Endpoints

The key secondary endpoints which are expressed as proportions such as EASI-75, and the proportion of participants achieving a 4-point improvement from baseline in the severity of Peak Pruritus NRS measure will be analyzed using the same method as for the co-primary

endpoints. This would also apply to any other binary endpoint in the study, such as the proportion of participants with PtGA of AD of clear (0) or almost clear (1) and ≥ 2 point improvement from baseline over 12 weeks. All binary secondary endpoints are based on responder definitions and the primary analysis is estimating a composite estimand. So missing responses would be defined as “non-response” while defining the binary outcomes.

For continuous endpoints, and change from baseline in the pruritus severity and frequency using the NRS measure at all scheduled time points, a mixed-effect model with repeated measures (MMRM) will be used. This model will include the factors (fixed effects) for treatment group, disease severity group, visit, treatment-by-visit interaction, and relevant baseline value. Within the framework of MMRM, the treatment difference will be tested at the pre-specified primary time point, Week 12, as well as at the other time points by time point-specific contrasts from the MMRM model. The primary analysis of all continuous secondary endpoints is estimating a hypothetical estimand and so no imputations for missing data will be used. The MMRM methodology as mentioned above will be used under an assumption that missing data is Missing At Random (MAR).

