2. INTRODUCTION

This statistical analysis plan (SAP) provides the detailed methodology for summary and statistical analyses of the data collected in Study B7451036. This document may modify the plans outlined in the protocol; however, any major modifications of the primary endpoint definition or its analysis will also be reflected in a protocol amendment.

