2.1.3. Additional Estimand(s)

2.1.3.1. Treatment Policy Estimand (Estimand 3)

A supplemental analysis of the co-primary endpoints will be based on the treatment policy estimand as described below:

- Population: Participants with moderate-to-severe AD as defined by the inclusion criteria to reflect the targeted participant population;
- Variable: Response based on IGA at Week 12;
- Intercurrent event: All data collected will be utilized;
- Population-level summary: Proportion of participants who are responders in each treatment group and differences in proportions of responders between each PF-04965842 dose and placebo.

Response based on EASI-75 at Week 12 will follow the same structure as defined for IGA.

[figure not shown]

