6.2. Secondary Endpoint(s)

6.2.1. Key Secondary Endpoint - Weeks 2, 4, and 12 Peak Pruritus NRS4 Response

- Estimand strategy: Composite, Estimand 1 (Section 2.1.1).
- Analysis set: FAS (Section 4).
- Analysis methodology: CMH and normal approximation in Section 5.2.1. Participants must have baseline PP-NRS ≥ 4 to be included in the analysis.
- Intercurrent events and missing data: The intercurrent event is captured through the variable definition; for participants who drop out for any reason, the response will be defined as “non-responsive” after that point.
- The number of participants, number and percent of response at each specified timepoints along with the 95% confidence interval by normal approximation will be presented for each treatment arm.
- The CMH test p-value, the estimate of the difference in proportions of response at each specified timepoints along with the corresponding 95% confidence interval by CMH normal approximation will be presented for each PF-04965842 dose group versus placebo.

6.2.2. Key Secondary Endpoint - Change from Baseline in PSAAD at Week 12

- Estimand strategy: Hypothetical, Estimand 2 (Section 2.1.2).
- Analysis set: FAS (Section 4). Participants must have observed baseline measure to be included in the analysis.
- Analysis methodology: MMRM in Section 5.2.3 including change from baseline data for each Week from Weeks 1 – 12.
- Intercurrent events and missing data: All data collected will be utilized; a simple average of the available values recorded within a week will be used for the analysis as a weekly measure; if there’s no available values recorded within a week, PSAAD for the week is missing and will not be used for analysis.
- Number of participants included in the analysis will be presented for each treatment arm.
- The least square mean (LSM) of change from baseline in PSAAD along with the corresponding 95% confidence interval will be presented for each treatment arm at each Week.

- The LSM difference along with the corresponding p-value and 95% confidence interval will be presented for each PF-04965842 dose group versus placebo arm at each Week.

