6.2.3.3. Continuous Endpoints

- Endpoints:
 - Weeks 2, 4, 8 and 12 Change from Baseline and Percent Change from Baseline in %BSA;
 - Weeks 2, 4, 8 and 12 Percent Change from Baseline in EASI;
 - Weeks 2, 4, 8 and 12 Change from Baseline and Percent Change from Baseline in Total SCORAD score, SCORAD subjective assessments of sleep loss (VAS);
 - Percent Change from Baseline in PP-NRS from Days 2-15, Weeks 4, 8 and 12.
- Estimand strategy: Hypothetical, Estimand 2 (Section 2.1.2).
- Analysis set: FAS (Section 4). Participants must have observed baseline measure to be included in the corresponding analysis.
- Analysis methodology: MMRM in Section 5.2.3.
- Intercurrent events and missing data: All data collected will be utilized.
- Number of participants included in the analysis will be presented for each treatment arm.
- The least square mean (LSM) of change from baseline or percentage change from baseline along with the corresponding 95% confidence interval will be presented for each treatment arm at each specified time points.

- The LSM difference along with the corresponding p-value and 95% confidence interval will be presented for each PF-04965842 dose group versus placebo arm at each specified time points.

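### SAP Estimand 2 is labelled hypothetical but keeps all data after treatment discontinuation, which is the SAP's treatment-policy rule and the opposite of protocol 9.1.1

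*SAP*

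**What the plan says.** SAP 2.1.2.1 calls Estimand 2 hypothetical: it "estimates the effect as if all patients maintain their randomized treatment". Under the intercurrent-event attribute the same section has "Intercurrent event: All data collected will be utilized". SAP 2.1.3.1 gives Estimand 3 the identical rule and introduces it this way: "A supplemental analysis of the co-primary endpoints will be based on the treatment policy estimand as described below".

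The pairing of hypothetical label and all-data rule returns in the analysis sections. SAP 6.2.2 (PSAAD) reads "All data collected will be utilized; a simple average of the available values recorded within a week will be used for the" weekly value. SAP 6.2.3.3 (other continuous efficacy endpoints) and 6.2.4.1 (continuous patient-reported outcomes) also cite Estimand 2 and use all data. SAP 6.2.4.2 (Peds FACIT-F) names no estimand but has the same rule, and 2.1.2.1 lists Peds FACIT-F under Estimand 2.

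Protocol 9.1.1 gives its hypothetical estimand the opposite rule: "All data after an intercurrent event (eg discontinuation of treatment), if collected, will be censored". Protocol 9.4.2.2 confirms the target: "The primary analysis of all continuous secondary endpoints is estimating a hypothetical estimand". The SAP introduction reserves the right to differ: "This document may modify the plans outlined in the protocol".

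**The concern.** A hypothetical strategy asks what would have happened had participants stayed on drug, so values observed after stopping drug do not belong in its estimate. A treatment-policy strategy uses them by design. One data rule cannot serve both. Taken literally, the SAP keeps any off-drug values and then reports the result as the on-treatment effect.

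PSAAD change at Week 12 is a key secondary endpoint inside the multiplicity procedure of SAP 5.1. The other Estimand 2 endpoints are tested at nominal 5%. What is at stake is mainly whether the reported effect is the one described, and whether the analysis dataset is built to the SAP's wording or to the protocol's.

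**Working it through.** **Plan's own figures.** The documents state no power for any Estimand 2 endpoint. The stated figures belong to the co-primary endpoints (75 per arm, two-sided 5%): at least 80% for IGA 12% vs 32%, and at least 96% for EASI-75 23% vs 53%. Fisher's exact test reproduces them as 80.7% and 96.1%. This point does not change them.

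**Step 1: the rules side by side.**

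| Place | Strategy named | Data after stopping drug |
|---|---|---|
| SAP 2.1.2.1, Estimand 2 | hypothetical | used |
| SAP 2.1.3.1, Estimand 3 | treatment policy | used |
| Protocol 9.1.1, secondary estimand | hypothetical | censored |

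SAP 5.2.3 (MMRM) and 5.3.2 (missing continuous data) contain no censoring step that would restore the protocol's rule.

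**Step 2: can off-drug values exist?** Protocol 7.1 separates stopping treatment from leaving the study and plans end-of-treatment assessments. Protocol Appendix 5 adds a 4-week follow-up. The Schedule of Activities places Visit 9 four weeks after the last dose for early terminators. So off-drug values are possible wherever an endpoint is scheduled at Visit 9.

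**Step 3: where would Visit 9 fall?** SAP Appendix 2 assigns visits by study day only. Week 12 is Days 72-99, the visit nearest the target day is kept, and ties go to the later visit. Let L be the last-dose day (1-84), with the early-termination visit on Day L and Visit 9 on Day L + 28.

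- L + 28 lies in 72-99 when L = 44-71: 28 days, and 28/84 = 33%. Visit 9 is then the kept Week 12 value.
- L = 16-43 (28 days) makes Visit 9 the Week 8 value.
- L = 1-15 (15 days) makes Visit 9 the Week 4 value.
- With the early-termination visit 0-7 days after the last dose and Visit 9 at +25, +28 or +31 days, the Week 12 count is n = 23-28 days (27-33%).

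**Step 4: direct dilution at Week 12.** Let D be the early discontinuation rate, with stopping spread evenly over Days 1-84, and f the share of the effect lost off drug. The documents give none of these, so all are assumptions. Off-drug share d = D × n/84; dilution = d × f, with f = 0.5-1.0.

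| D | d, n = 23 | dilution | d, n = 28 | dilution |
|---|---|---|---|---|
| 5% | 1.37% | 0.68-1.37% | 1.67% | 0.83-1.67% |
| 10% | 2.74% | 1.37-2.74% | 3.33% | 1.67-3.33% |
| 15% | 4.11% | 2.05-4.11% | 5.00% | 2.5-5.0% |

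At D = 15% this is 75 × 0.0411 = 3.1 to 75 × 0.05 = 3.75 participants per arm. At D = 0 it is zero.

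**Step 5: carry-through from earlier visits.** Step 4 ignores off-drug values at Weeks 4 and 8, which also inform Week 12 in an MMRM. A simulation indicates their weight. It used 20,000 per arm, values every two weeks to Week 12, within-subject correlation 0.6, a full standardized effect of 0.5 lost at once on stopping, equal dropout in the arms, four further weeks of off-drug data, and a multivariate-normal likelihood fit standing in for the MMRM.

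| D | Censored | All data | Shrinkage |
|---|---|---|---|
| 5% | 0.523 | 0.506 | 1 - 0.506/0.523 = 3.3% |
| 10% | 0.484 | 0.447 | 1 - 0.447/0.484 = 7.6% |
| 20% | 0.513 | 0.444 | 1 - 0.444/0.513 = 13.5% |

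The censored estimates scatter around 0.5 from simulation error, so the ratios are approximate. The assumed off-drug data are richer than a single Visit 9. The table shows direction and order of size and is not a prediction for this trial.

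**The case against.** **The all-data sentence may be boilerplate for no imputation.** SAP 6.2.3.4 uses it for corticosteroid-free days, which are counted only within the treatment exposure period, and SAP Appendix 1 codes the MMRM endpoints as observed data. This weakens the section 6 repetitions as evidence. It does not rescue 2.1.2.1, where the sentence is the intercurrent-event attribute of the estimand and matches Estimand 3 word for word.

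**The SAP may depart from the protocol.** This stands: the difference from 9.1.1 alone is not a breach. It does not cure the conflict within the SAP, and the SAP's version history records no change of rule in 2.1.2 that would show a deliberate switch.

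**There may be no off-drug values.** This stands as a condition. The available text of the Schedule of Activities has broken columns. The patient-reported outcome rows appear to be marked at follow-up, but the IGA, EASI and SCORAD rows cannot be read with confidence. If nothing is collected off drug, the MMRM under missing at random fits the label.

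**Stronger readings that the documents do not support.**

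- A reader might infer type I error inflation. If the effect wanes off drug, the retained values pull the active arms toward placebo, and nothing in the documents points the other way.
- A reader might turn the dilution into a power loss. Censoring discards those same values and so also costs precision, and no effect size or standard deviation is given for any Estimand 2 endpoint.
- A reader might extend the point to the co-primary and other binary endpoints. They fall under Estimand 1, which has its own non-responder rule, and how follow-up visits are windowed there is a separate question.
- A reader might prefer to relabel Estimand 2 as treatment policy. That would need a protocol change, and it fits poorly because only an end-of-treatment visit and a 4-week follow-up are planned after stopping drug, not collection through Week 12.

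**Conclusion.** The point holds and should be fixed. Confidence is high for the wording conflict: Estimand 2 has a hypothetical label and a treatment-policy rule, against protocol 9.1.1.

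The consequence depends on whether off-drug values are collected. If they are not, it is zero. If they are, the likely result is modest dilution toward no effect in visit-based endpoints measured at Visit 9. Direct substitution at Week 12 gives 0-5% for D of 0-15%, and carry-through could raise this. Small is a fair description at low discontinuation but is not assured near 20%. These sizes rest on assumed discontinuation rate, timing and loss of effect.

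For PSAAD the size cannot be given. Whether the symptom diary continues after stopping drug cannot be read from the documents, and SAP Appendix 2 defines no weekly windows. The sample size and the stated co-primary power do not change.

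**What to change.** Before unblinding, replace the all-data rule in SAP 2.1.2.1, 6.2.2, 6.2.3.3, 6.2.4.1 and 6.2.4.2 with that of protocol 9.1.1:

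- Set values after permanent discontinuation of study treatment to missing.
- Do not map a post-treatment Visit 9 into the Week 4, 8 or 12 window.
- State a day limit after the last dose within which the end-of-treatment or early-termination assessment counts as on-treatment. The protocol's rule does not say this, and it cannot be programmed without it.
- Then analyse by MMRM, or by ANCOVA for Peds FACIT-F, under missing at random.

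An all-data analysis may be kept as supplementary, labelled as such.

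The cost is wording in five SAP sections, the windowing and day-limit statements, and one data filter tied to the last-dose date. It needs no new data collection, no change in sample size and no protocol amendment, since it adopts the protocol's own rule.

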2.1.3. Additional Estimand(s)

2.1.3.1. Treatment Policy Estimand (Estimand 3)

A supplemental analysis of the co-primary endpoints will be based on the treatment policy estimand as described below:

- Population: Participants with moderate-to-severe AD as defined by the inclusion criteria to reflect the targeted participant population;
- Variable: Response based on IGA at Week 12;
- Intercurrent event: All data collected will be utilized;
- Population-level summary: Proportion of participants who are responders in each treatment group and differences in proportions of responders between each PF-04965842 dose and placebo.

Response based on EASI-75 at Week 12 will follow the same structure as defined for IGA.

[figure not shown]
2.2. Study Design

This is a randomized, double blind, placebo controlled, parallel group, Phase 3 study to evaluate the efficacy and safety of PF-04965842 in adolescent participants 12 to <18 years of age with moderate-to-severe AD co administered with background topical therapy. A total of approximately 225 participants will be enrolled from approximately 100 sites located globally. Participants will be randomized in a 1:1:1 ratio to receive 200 mg PF-04965842 (N=75) or 100 mg PF-04965842 QD (N=75) or matching placebo (N=75) from Day 1. Randomization will be stratified by baseline disease severity (moderate [IGA = 3] vs. severe [IGA = 4] AD). The treatment period is 12 weeks.

In a sub-study, up to approximately 90 participants (up to 30 in each respective study group) who have completed 8 weeks of treatment with study intervention will receive a tetanus, diphtheria and pertussis combination vaccine (Tdap) at Week 8, and will have blood samples collected for the evaluation of immunogenicity to the vaccine at Weeks 8 and 12. The participants in the immunogenicity sub-study will complete all other protocol-specified procedures in the main study. A study design schematic is presented in Figure 1.

Qualified participants completing 12-week treatment with study intervention will have the option to enter the long-term extension (LTE) study B7451015. Participants discontinuing early from the study will undergo a 4 week follow up.

Figure 1. Study Design

Intervention Groups and Duration:

Eligible participants will be randomized into 3 intervention groups in the main study:

Group 1 (N=75): 200 mg PF-04965842 once daily (QD) for 12 weeks (Sub-study: N=up to 30, Tdap vaccination at Week 8).

Group 2 (N=75): 100 mg PF-04965842 QD for 12 weeks (Sub-study: N=up to 30, Tdap vaccination at Week 8).

Group 3 (N=75): placebo QD for 12 weeks (Sub-study: N=up to 30, Tdap vaccination at Week 8).

090177e19618b8f5\Approved\Approved On: 25-Jan-2021 08:47 (GMT)

Sample Size Determination

A total sample of 225 participants, with 75 participants randomized to PF-04965842 200 mg QD, 75 participants randomized to PF-04965842 100 mg QD, 75 participants randomized to matching placebo (1:1:1 randomization) is planned. This would provide at least 80% power to detect a difference of at least 20% in IGA response rate between either dose of PF-04965842 and placebo, assuming the placebo response rate is 12% at Week 12. This will also provide at least 96% power to detect a difference of at least 30% in EASI-75 response rate between either dose of PF-04965842 and placebo, assuming the placebo response rate is 23% at Week 12.

For a given dose (PF-04965842 200 mg QD or 100 mg QD), both co-primary endpoints must achieve statistical significance to meet the primary objective.

The familywise Type I error rate (for testing the co-primary and key secondary endpoints) will be strongly controlled at 5% (2-sided) using a closed-testing method based on a sequential, iterative Bonferroni type approach as outlined in Section 5.1.

3. ENDPOINTS AND BASELINE VARIABLES: DEFINITIONS AND CONVENTIONS

3.1. Primary Endpoint(s)

The co-primary efficacy endpoints are:

- IGA response: Response based on the IGA score of clear (0) or almost clear (1); and a reduction from baseline of ≥ 2 points at Week 12.
- EASI-75 response: Response based on the EASI $\geq 75\%$ improvement from baseline (EASI-75) at Week 12.

Detailed descriptions of how the IGA and the EASI scores are derived are provided in Appendix 4 and Appendix 5 respectively.

